Patients will be recruited from the inpatient services and outpatient clinics of the University of Oklahoma Health Sciences Center. A meeting with all study personnel to review the study protocol will be held before initiation of the study, as well as every 3-6 months, depending on study progress. Informed consent will be obtained prior to enrollment in the study. The randomization schedule will be implemented with the use of concealed envelopes and it will be stratified by sex. Blocked randomization will be used to decrease the chance of imbalances in the two groups over time.

After informed consent and screening procedures are completed, all patients will undergo noninvasive continuous ECG monitoring for 2 weeks to evaluate their AF burden (the percent of time spent in AF) using an adhesive waterproof continuous monitoring patch (Zio[®] Patch). The Zio[®] Patch (iRhythm Technologies, Inc) is an FDA approved, single-lead, lightweight, 14-day ambulatory ECG adhesive patch monitor. The patch is well tolerated and allows significantly longer continuous monitoring than a regular Holter monitor, leading to an improved AF detection rate ³⁴. After the 2-week monitoring period, patients will be randomly assigned (1:1) to active or sham LLTS. Patients will be blinded to the treatment allocation, and every effort will be made to conceal from the study personnel the nature of the intervention in each study arm. Blinding of the patients will be accomplished by having a sham control arm, in which stimulation will be delivered to a different site (the ear lobe), devoid of vagal innervation ³⁵. By doing so, all patients will be aware that they are receiving stimulation, but they will not be told which site achieves active VN

stimulation. The patients will be requested to refrain from discussing the details of their treatment with other patients in the clinic and with the physicians, nurses and the rest of clinic staff. The clinical coordinator and a clinic physician who will not participate in any of the other study related assessments will be unblinded to the treatment allocation and will instruct the patients on the proper use of the device. These study personnel will be designated to address the patients' questions and concerns as well as to record any side effects related to the use of the device.

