The primary outcome of this study is the percent of time spent in AF over the monitoring period (AF burden) at the 6-month time point. Secondary outcomes include total duration of AF over the 2-week monitoring period, longest daily duration of AF, measures of HRV and serum cytokine levels. Outcomes will be compared between groups using a Generalized Estimating Equations modeling approach, with 3 time points (baseline, 3 months, 6 months) and 4 terms included in the model (group effect, time effect, group by time interaction, adjustment for baseline measure).

Significant interactions will be followed by time trend analyses stratified by intervention group. If the interaction is not significant, the interaction term will be dropped from the model and the between-group comparisons will be made by combining the 3-month and 6-month data. For all pair-wise testing, we will adjust for multiple comparisons using Tukey's method. The modeling assumptions will be evaluated by plotting the residuals by the predicted values (for the constant variance assumption) and comparing the normal QQ plot with the QQ plot of the residuals (for the normality assumption). If the modeling assumptions are not satisfied, we will perform a natural log transformation of the data, to better satisfy these assumptions. For 0 values, a value of 0.01 will be added to each measure before applying the natural log. Analyses will be based on the intention-to-treat principle. In post-hoc exploratory analyses, we will use logistic regression analysis to identify predictors of clinical and cytokine response to LLTS, defined as a decrease of AF burden and a decrease in cytokines at 6-month follow-up, respectively. Those variables that which are associated with response to LLTS in univariate analysis at p<0.1 will be entered into a multivariate logistic regression model, using a backward elimination method to identify the most parsimonious model. In light of the limited sample size, such analyses will be underpowered and will be considered hypothesis-generating only. Statistical significance will be declared at p<0.05.

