Sample size and power calculations: For purposes of sample size calculations we have simplified the analysis to focus on the AF burden at the 6-month time point between the 2 groups. Assuming a mean±standard deviation AF burden in the control group of $28.4\pm31.2\%$ ³⁴ and a 87% reduction in the LLTS group to 3.7% (assuming a common standard deviation of 31.2%), 26 patients per group would provide 80% power to detect the specified effect sizes at a two-sided significance α level of 0.05. Approximately 30 patients with paroxysmal AF are seen in our clinics each month. Assuming that 1 out of 4 eligible patients would agree to participate in the study, we should be able to enroll the required number of patients within the proposed 17 months, allowing for 6 months of additional follow up and a final month for data analysis.

F. Gender/Minority/Pediatric Inclusion for Research

Participants will be age 21 or older. Race, minority status and gender will not affect enrollment.

[figure not shown]
G. Human participants

The study population will include 52 male/female patients with paroxysmal AF, aged 21 or older, including all races. Since AF is extremely rare in patients less than 21 years old, this age limit is not expected to affect the overall results.

Inclusion Criteria:

- 1. Male and female patients older than 21 year old
- 2. Paroxysmal AF

Exclusion Criteria:

- 1. Left ventricular dysfunction (Left ventricular ejection fraction <40%)
- 2. Significant valvular disorder (i.e., prosthetic valve or hemodynamically relevant valvular diseases)
- 3. Recent (<6 months) stroke or myocardial infarction
- 4. Severe heart failure (NYHA IV)
- 5. Left atrial dilatation (>55mm)
- 6. Recurrent vaso-vagal syncopal episodes
- 7. Unilateral or bilateral vagotomy
- 8. Pregnancy or breast feeding
- 9. Sick sinus syndrome, 2nd or 3rd degree AV block, bifascicular block or prolonged (PR>300ms) 1st degree AV block.
- 2. Identify sources of research material in the form of specimens, records or data.

The research information will consist of the AF burden and serum inflammatory cytokines at each time point specified in the protocol (see Figure 4).

- 3. Describe plans for recruitment and consent procedures to be followed.
- a. Describe the location where consent is most likely to take place (will consent be obtained while an inpatient, in the ER/ICU, will consents be mailed with follow-up meeting to discuss the consent, etc.).

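### Randomisation is stratified by sex but the four-term GEE leaves sex out, so its standard error may be somewhat too large

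*Combined protocol and SAP*

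**What the plan says.** Section D, under Specific Aim 1, describes the allocation: "The randomization schedule will be implemented with the use of concealed envelopes and it will be stratified by sex". It continues: "Blocked randomization will be used to decrease the chance of imbalances in the two groups over time". The ratio is equal: "patients will be randomly assigned (1:1) to active or sham LLTS". Sex is the only stratification factor named, and the block size is not given.

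Section E specifies a "Generalized Estimating Equations modeling approach, with 3 time points (baseline, 3 months, 6 months) and 4 terms included in the model", and lists those terms as "group effect, time effect, group by time interaction, adjustment for baseline measure". This is a closed, counted list, so the absence of sex is not a matter of reading silence. The same model serves the primary outcome (AF burden at 6 months) and the secondary outcomes. Section E names neither the type of standard error nor the working correlation.

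The sample size paragraph in Section E rests on a plain two-group comparison at 6 months: "87% reduction in the LLTS group to 3.7% (assuming a common standard deviation of 31.2%), 26 patients per group would provide 80% power".

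**The concern.** Stratified blocking makes the arms nearly equal in their sex mix, so differences between men and women largely cancel out of the treatment contrast, and its true variance falls accordingly. An analysis that omits sex does not register this: it leaves the between-sex variation in the residual and reports a standard error for a design that had not been balanced.

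This has a consequence only if sex predicts the outcome after baseline is in the model. The interval is then too wide, the test rejects less often than 5% under the null, and part of the precision bought by stratifying goes unused in a trial of 52 patients. There is no bias. If sex acts only through baseline AF burden, or not at all, nothing is lost.

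**Working it through.** **1. The plan's own figure.** Inputs from the sample size paragraph: means 28.4 and 3.7, common SD 31.2, two-sided α 0.05, 80% power.

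- Difference: 28.4 − 3.7 = 24.7 points.
- n per group = 2 × (1.960 + 0.842)² × 31.2² / 24.7² ≈ 25.1, rounded up to 26. The stated figure reproduces.
- At n = 26 the SE is 31.2 × √(2/26) = 8.65, and power is Φ(24.7/8.65 − 1.96) = 81.4% (79.9% with the t distribution).

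**2. Closed form for the excess.** Let σ be the outcome SD after baseline adjustment and R² the share of σ² explained by sex. Omitting sex, the model reports σ√(2/26). With exact balance within sex, the true SE is σ√(1 − R²)·√(2/26). The ratio is 1/√(1 − R²), and the actual two-sided size is 2{1 − Φ(1.96/√(1 − R²))}. For R² of 2, 5, 10 and 20% this gives:

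- SE excess: 1.0, 2.6, 5.4 and 11.8%
- actual size: 4.8, 4.4, 3.9 and 2.8%

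**3. What R² means in points.** Assume a baseline to 6-month correlation of 0.5 and 40% women; neither is in the documents. Residual variance is 31.2² × (1 − 0.5²) = 730. The difference between men and women after baseline adjustment is √(R² × 730 / (0.4 × 0.6)), shown in the table.

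**4. Simulation of the 6-month comparison adjusted for baseline.** 52 patients, blocks of 4 within sex (assumed), the assumptions of step 3, normal outcomes, no missing data, 60,000 runs per setting, model-based SE with t reference. The mean reported SE without sex was 7.54 to 7.55 throughout, close to 31.2 × √0.75 × √(2/26) = 7.49. Power is at 24.7 points.

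| R² | Sex difference (points) | True SD of estimate | Type I error, sex omitted | Power without / with sex |
|---|---|---|---|---|
| 2% | 7.8 | 7.52 | 4.8% | 89.3 / 89.6% |
| 5% | 12.3 | 7.37 | 4.5% | 89.9 / 90.7% |
| 10% | 17.4 | 7.19 | 3.8% | 90.2 / 92.0% |
| 20% | 24.7 | 6.83 | 3.0% | 91.3 / 94.5% |

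Adding sex returned type I error to 4.8 to 5.0%. At R² = 0 adding sex cost 0.1 point of power. With sex acting only through baseline (10% of baseline variance; 20,000 runs), type I error was 5.1% either way.

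**5. The planned type of model.** An exchangeable GEE on the 3- and 6-month data, with group, time, interaction and baseline, was simulated with 8,000 null runs per setting. Type I error, sex omitted:

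| R² | Model-based, t | Mancl-DeRouen, t | Uncorrected sandwich, 1.96 |
|---|---|---|---|
| 0 | 5.3% | 4.8% | 6.8% |
| 2% | 4.9% | 4.5% | 6.0% |
| 5% | 4.1% | 3.7% | 5.6% |
| 10% | 3.4% | 3.0% | 4.6% |
| 20% | 2.9% | 2.7% | 4.0% |

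With sex added, the model-based test ran at 4.5 to 5.4% and the uncorrected sandwich at 6.1 to 7.1%. At R² 10% and 24.7 points, model-based power was 90.5% without sex and 92.0% with it. If the true difference were 20 points, it was 75.2 against 78.8% at R² 10%, and 77.3 against 83.8% at 20% (5,000 runs each).

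**6. Why the SE type belongs here.** With 52 patients the uncorrected sandwich ran about 4% below the true SD at R² = 0. That shortfall cancels the excess from omitting sex somewhere between R² of 5 and 10%. Adding sex removes the excess and leaves the shortfall exposed.

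**The case against.** The best case against the point is that it is small and errs on the safe side. The estimate is unbiased, type I error is not inflated from this source, and under the assumptions above power at the planned effect is already about 89 to 91% without sex. R² is unknown, and the larger rows need a lot: 20% means a sex difference beyond baseline as large as the planned treatment effect, and 10% means 17.4/24.7 = 70% of it. At 2 to 5% the gain is under one point of power. This stands: the 20% row is an outer limit, not an expectation.

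A second objection is that the choice of SE is a separate issue and, at low R², matters at least as much as sex. That is fair, but it is a reason to settle both together, since adding sex alone does not bring the uncorrected sandwich to 5%. The size also depends on which correction is used. An HC2-type sandwich matched the model-based result within 0.1 point with sex omitted, while Mancl-DeRouen was 0.2 to 0.5 point more conservative. A model-based SE further depends on the working correlation, which the plan does not state.

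Third, the simulations use normal outcomes. AF burden cannot go below 0 and its assumed SD (31.2) exceeds its mean (28.4). Section E also allows a log transformation, and pooling of the 3- and 6-month data if the interaction is not significant. The decimals are therefore indicative. The direction follows from the balanced design and does not depend on normality.

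**Conclusion.** The point holds as a refinement to consider; it does not threaten validity. The trial balances on sex and then analyses as if it had not. If sex predicts the 6-month outcome beyond baseline, a model-based or small-sample-corrected SE is too large: by up to about 5% for R² of 10% or less, and by about 11% at 20%. The test is correspondingly conservative. At the planned difference the power forgone is about 0.3, 0.8, 1.8 and 3.2 points at R² of 2, 5, 10 and 20%, and it is larger if the true effect is smaller than planned.

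These sizes rest on assumed values for R², block size, sex mix and baseline correlation. Whether sex predicts the secondary outcomes cannot be judged from the documents.

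**What to change.** In Section E, add sex, as the randomisation stratum, to the GEE as a fixed covariate for the primary and secondary outcomes. In the same place, state that inference will use a model-based or a named small-sample-corrected SE with a t reference. If the model-based SE is chosen, name the working correlation too.

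The cost is one model term, one degree of freedom and a sentence or two. Sex is already recorded for the randomisation and N stays at 52. If sex proves unrelated to the outcome, the loss is about 0.1 point of power. Fixing this before unblinding also removes any later choice between results with and without sex.

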sinus rhythm for AF ablation, were randomized to either 1 hour of LLTS (n=20) or control (n=20). LLTS in the right ear, 50% lower than the voltage that slowed the sinus rate, was accomplished by attaching a flat metal clip onto the tragus. Under general anesthesia, AF was induced at baseline and after 1 hour of LLTS or sham stimulation and were analyzed for inflammatory cytokines, including TNF α and CRP, using a multiplex immunoassay. Pacing-induced AF duration decreased significantly by 6.3±1.9 min compared to baseline in the LLTS group, but not in the control (p=0.002 for comparison between groups; Figure 2A). AF cycle length increased significantly from baseline by 28.8±6.5ms in the LLTS group, but not in the control (p=0.0002 for comparison between groups). Systemic (femoral vein) but not coronary sinus TNF α and CRP levels decreased significantly only in the LLTS group (Figure 2B). Importantly, the magnitude of decrease in TNF- α levels by LLTS was comparable with the difference between patients with active vs. inactive inflammatory diseases ³³. We concluded that LLTS acutely suppresses AF and decreases inflammatory cytokines in patients with paroxysmal AF, supporting the emerging paradigm of

neuromodulation to treat AF ³⁰. The results of this study were published in the Journal of the American College of Cardiology ³⁰.

D. Research design and Methods

Specific Aim 1: To examine the effect of intermittent (1 hour daily) LLTS on AF burden in patients with paroxysmal AF over a 6-month period.

This is a prospective double-blind randomized controlled study. Patients with paroxysmal AF, documented by ECG, pacemaker/implantable cardioverter defibrillator (ICD) electrogram or Holter monitor, within 3 months of randomization on 2 separate occasions, at least 1 day apart, of at least 30 seconds duration, will be eligible for inclusion in the study.

Patients will be excluded if they have any of the following:

- 1. Left ventricular dysfunction (Left ventricular ejection fraction <40%)
- 2. Significant valvular disorder (i.e., prosthetic valve or hemodynamically relevant valvular diseases)
- 3. Recent (<6 months) stroke or myocardial infarction
- 4. Severe heart failure (NYHA IV)
- 5. Left atrial dilatation (>55mm)
- 6. Recurrent vaso-vagal syncopal episodes
- 7. Unilateral or bilateral vagotomy
- 8. Sick sinus syndrome, 2nd or 3rd degree AV block, bifascicular block or prolonged (PR>300ms) 1st degree AV block

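### Patients with no AF on the baseline patch can be randomised, and the exploratory response analysis then counts them as non-responders by construction

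*Combined protocol and SAP*

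**What the plan says.** Section D, Specific Aim 1, admits patients whose AF was documented "within 3 months of randomization on 2 separate occasions, at least 1 day apart, of at least 30 seconds duration". The inclusion list in Section G asks only for age and paroxysmal AF. Neither exclusion list mentions burden.

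Every patient wears a 2-week patch after screening, so that burden can be measured. Then, in Section D, "After the 2-week monitoring period, patients will be randomly assigned (1:1) to active or sham LLTS". Randomisation is blocked and stratified by sex only.

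In Section E the primary outcome is AF burden at 6 months, compared between arms in a model that adjusts for the baseline measure. Zeros are foreseen: if the data need a log transformation, 0.01 is added first. In the post-hoc logistic regression, clinical and cytokine response are "defined as a decrease of AF burden and a decrease in cytokines at 6-month follow-up, respectively". Variables with univariate p<0.1 enter a multivariable model with backward elimination. The plan calls these analyses underpowered and hypothesis-generating.

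The sample-size paragraph compares 6-month burden between arms, 28.4% against 3.7% with a common SD of 31.2%, and states that "26 patients per group would provide 80% power to detect the specified effect sizes". The 28.4% and its SD come from a cited pilot study of patch monitoring. The plan does not say whether that study's mean included patients with no recorded AF.

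**The concern.** AF burden cannot go below 0%. A patient with a clean baseline patch can stay at 0% or rise, but cannot decrease. The response definition therefore fixes this patient's outcome before treatment starts. In a model meant to find who responds to LLTS, baseline burden, and anything correlated with it, can look predictive only because of the definition.

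Whether AF was seen on the baseline patch is also likely to be prognostic for the 6-month burden. It is measured before randomisation but not used in it, so with 26 patients per arm the clean-patch patients can fall unevenly.

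The same observation raises a question about power: does a control mean of 28.4% fit patients admitted on two 30-second episodes?

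**Working it through.** **1. Can a zero-burden patient be randomised?** Nothing in the criteria prevents it. The documented minimum is 2 × 30 s = 60 s of AF. As a burden this is 60 / (90 × 86,400) = 0.00077% over 90 days, or 60 / (14 × 86,400) = 0.005% if both episodes fell within one 14-day patch. If episodes followed a Poisson process with k per 90 days (an assumption), the chance of a clean patch is exp(−14k/90): 73% at k=2, 54% at k=4, 39% at k=6, 21% at k=10. The k=2 value is a worst case: ECGs and Holter recordings see only part of the 3 months, so two documented episodes are a lower bound on what occurred.

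**2. Response coding.** Response requires 6-month burden minus baseline burden to be below 0. With baseline 0 and 6-month burden at least 0, the difference is never negative, so the probability of response is 0 under any treatment effect. With a share z at zero, the response rate cannot exceed 1 − z. Among 26 LLTS patients, those fixed as non-responders number 26z: 2.6 at z=10%, 5.2 at 20%, 7.8 at 30% (z is assumed; the documents give none). In the logistic model the group with no AF at baseline has no events.

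**3. Chance imbalance.** Assume 16 of 52 patients have a clean patch and allocation ignores this. For a 26/26 split (hypergeometric, ignoring sex strata and blocks), the probability that the arms differ by 4 or more is 0.368, or 37%.

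**4. The stated power.** Difference 28.4 − 3.7 = 24.7; SD 31.2; 26 per arm; two-sided 0.05. The noncentral t gives 79.9% and the normal approximation 81.4%. The plan's figure reproduces.

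**5. When would power fall?** Suppose a share p has zero burden at 6 months in both arms and the plan's means describe only the rest. Then the difference is (1−p) × 24.7, and an arm with mean m among the rest has mixture SD √[(1−p)(31.2² + m²) − ((1−p)m)²]. Column A gives the control-mixture SD to both arms. Column B uses each arm's own mixture SD. Column C uses the control-mixture SD for sham and an assumed LLTS SD of 15 throughout, because 31.2 is impossible at a mean of 3.7% on a 0–100% scale: the maximum is √(3.7 × 96.3) = 18.9.

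| p | Difference | Control SD | A | B | C |
|---|---|---|---|---|---|
| 0 | 24.7 | 31.2 | 79.9% | 79.9% | 95% |
| 10% | 22.2 | 30.8 | 72% | 74% | 90% |
| 20% | 19.8 | 30.1 | 64% | 67% | 84% |
| 30% | 17.3 | 29.2 | 55% | 60% | 75% |

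If the 28.4% already averages over zero-burden patients and the 3.7% is reached, the difference stays 24.7 and nothing is lost.

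**6. Would excluding clean baseline patches protect power?** Take the four rates in step 1 in equal shares (an assumption), with q = exp(−14k/90). The share at zero on any patch without treatment is (0.733 + 0.537 + 0.393 + 0.211)/4 = 47%. Of patients with a clean baseline patch, Σq(1−q)/Σq = 45% show AF on a later sham patch. After exclusion, the share at zero at 6 months is Σq(1−q)/Σ(1−q) = 40%. By the column A formula, power moves from 41% to 47%.

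**The case against.** A reader might infer more: that patients with a clean baseline patch cannot contribute to the primary contrast, so the trial is underpowered and they must be excluded. The documents do not support that, for three reasons.

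- The primary outcome is 6-month burden between arms, and the 87% is a difference between group means, not a fall that each patient must show. Paroxysmal AF recurs, so a sham patient at 0% at baseline can have AF at 6 months.
- Dilution follows only if the 28.4% excludes zero-burden patients. The plan is silent, and the cited study is not available here.
- Step 6 shows that exclusion recovers little under a simple recurrence model, and it narrows the population from paroxysmal AF to AF visible on a 2-week recording.

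The defence also has force on the narrower point. The response analysis is post hoc and labelled hypothesis-generating. Adjustment for baseline burden already handles part of any chance imbalance, and the 37% rests on an assumed 16 of 52.

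These arguments limit the importance of the point but leave the coding error in place. An exploratory label does not make an impossible outcome informative, and adjustment in the primary model does not reach the logistic model. Nor would adjustment restore a mean difference if dilution did occur.

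**Conclusion.** The point holds for the response definition and, to a lesser degree, for stratification. Zero-burden patients can be randomised, and the AF-burden response rule misclassifies every one of them. This follows from the definition alone; only the number affected depends on an assumed share. The damage is confined to an exploratory analysis. The missing stratum leaves an avoidable imbalance that the primary model partly corrects.

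No defect in the 80% power is shown. What is missing is any statement that the 28.4% fits patients admitted under this entry rule. The losses in step 5 are conditional on zeros at 6 months in both arms and on a source mean that excludes them, and the result depends heavily on the LLTS SD.

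**What to change.** **Section E, exploratory analyses.** Add: *The analysis of predictors of AF-burden response will include only patients with baseline AF burden above 0%.* The cytokine response analysis is unaffected. The cost is a smaller exploratory sample. Patients with very low baseline burden still have little room to fall, so baseline burden should be interpreted cautiously as a predictor even then.

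**Section D, randomisation.** Replace stratification by sex with: *Randomisation will be stratified by sex and by whether any AF was recorded on the baseline patch.* This makes four strata in 52 patients, 13 on average, so block sizes must be small enough to avoid many incomplete blocks. The patch report must also be in hand before randomisation. The plan completes the recording by then but does not say that it has been read. The stratum addresses imbalance, not dilution.

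**Optional.** One sentence in the sample-size paragraph saying whether the 28.4% includes patients with no recorded AF, and what share is expected here, would settle the power question. Excluding patients with a clean baseline patch is for the sponsor to weigh. It would need 52/(1−p) monitored patients: 65 at 20% excluded, 87 at 40%. The plan's accrual figures imply 30 × 1/4 × 17 = 127.5, which treats all 30 patients seen each month as new and eligible.
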